7.5 SECONDARY ENDPOINTS

7.5.1 Key secondary endpoints

This section is not applicable as no key secondary endpoints have been specified in the protocol.

7.5.2 (Other) Secondary endpoints

Other secondary efficacy endpoints (all time to first event, measured from date of randomisation to end of observation period) are:

- A combined endpoint of DTE and unplanned revascularisation by PCI/CABG
- A combined endpoint of DTE
- Individual OEs:
 - All deaths
 - Cardiovascular death
 - Non-cardiovascular death
 - Undetermined
 - MI
 - Stroke
 - SE
 - Stent thrombosis (definite)

- Composite of death + MI + stroke
- Unplanned revascularisation by PCI/CABG

[figure not shown]
Time to first event endpoints will be analysed using the same methods as for the primary endpoint. However, comparisons will be for superiority of 110mg DE-DAT over warfarin-TAT, 150mg DE-DAT over warfarin-TAT and 150mg DE-DAT and 110mg DE-DAT combined over warfarin-TAT (for DTE/unplanned revascularisation and DTE, NI will be tested first). No multiplicity adjustments are planned for secondary endpoints, unless they are part of the hierarchical procedure (see [Section 7.4](#)). Nominal one-sided p-values will be reported for descriptive purposes. For analysis of stent thrombosis, Kaplan Meier plots will be provided additionally by stent type (DES, BMS,..) and by “Index PCI for ACS vs. elective index PCI (non-ACS)”.

Only positively adjudicated events will be included in the analyses. Secondary analyses will also include presentations of number (%) of patients with events.

All secondary analyses will be performed on the FAS. The robustness of these analyses will be assessed by on-treatment analyses of the TS.

Further sensitivity analyses will be performed on investigator reported events (i.e. those that are positively and negatively adjudicated). Post-treatment events will also be summarised and a summary of adjudication will be presented showing the number of investigator-reported OEs along with whether they were positively or negatively adjudicated or whether they were non-assessable.

Frequency counts will be provided showing the number of patients experiencing recurrent events by endpoint. The number of events will be presented as follows: the number of initial events, the number of additional events and the total number of events. Individual outcome events (with the exception of death), as described above, will be presented in these summaries.

7.7 EXTENT OF EXPOSURE

Duration of exposure is calculated in days as:

Date of last administration of trial medication – date of first administration of trial medication + 1.

If the date of the first intake of study medication is missing, the randomisation date will be used to calculate exposure.

Total treatment time therefore includes time when treatment was temporarily discontinued and subsequently reintroduced. Descriptive statistics and frequency counts as described in [Section 7](#) will be presented for extent of exposure. Categorisations for total treatment time are defined as follows:

- < 3 months
- 3 months - < 6 months
- 6 months - < 12 months
- 12 months - < 18 months
- 18 months - < 24 months
- 24 months - < 30 months
- ≥ 30 months

In addition, extent of exposure taking into account any temporary discontinuations in study medication will be computed (REP not included).

7.8 SAFETY ANALYSIS

This section describes the analysis of standard safety data such as adverse events, laboratory data, vital signs, ECGs, etc. The analysis of bleeding outcome event data is covered in [Section 7.6](#). All safety analyses will be performed on the TS (including the REP, where applicable).

7.8.1 Adverse events

The analyses of adverse events will be descriptive in nature. All analyses of AEs will be based on the number (and %) of patients with AEs and not on the number of AEs. In addition to the usual summaries of adverse events, some analyses will be based on the number of AEs per patient year.

Furthermore, for analysis of AE attributes such as duration, severity, etc. multiple AE occurrence data on the eCRF, will be collapsed into AE episodes provided that all of the following applies:

- The same MedDRA lowest level term was reported for the occurrences

- The occurrences were time-overlapping or time-adjacent (time-adjacency of 2 occurrences is given if the second occurrence started on the same day or on the day after the end of the first occurrence)
- Treatment did not change between the onset of the occurrences or treatment changed between the onset of the occurrences, but no deterioration was observed for the later occurrence

For further details on summarization of AE data, please refer to the guideline ‘Handling and summarization of adverse event data for clinical trial reports and integrated summaries’ [2].

The analysis of adverse events will be based on the concept of treatment emergent adverse events. Refer to [Section 6.1](#) for a full list of the different treatment periods to which adverse events will be assigned based on the onset date/time of the event. In general, adverse events attributed to ‘Screening’, ‘Post-treatment’ or ‘Post-study’ will be listed only.

An overall summary of adverse events will be presented.

Separate summaries will be created for patients with serious adverse events.

AEs will also be analysed with respect to drug relationship, worst intensity and discontinuations of study drug.

Adverse events per patient year will be summarised by treatment, primary system organ class (SOC) and preferred term (PT). The SOC's will be sorted according to the standard sort order specified by the European Agency for the Evaluation of Medicinal Products (EMA). The PTs will be sorted by descending incidence within SOC. The number of events per patient year is calculated per treatment arm as follows:

$$\frac{\text{total number of patients with AE} \times 365.25}{\text{number of days exposure}}$$

Further details will be provided in the technical TSAP (comprehensive list of tables, figures, and listings, example table and listing templates and ADS specifications).

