7.3 PLANNED ANALYSES

7.3.1 Primary analyses

The primary endpoint (measured from date of randomisation to end of observation period) is:

- Time to first MBE/CRNMBE

as determined by the IAC. It will be analysed using the stratified Cox proportional hazards regression model including factors for age (<80 or ≥80 years old) and treatment arm (110mg DE-DAT vs warfarin-TAT and 150mg DE-DAT vs warfarin-TAT). Models will be fitted for each comparison separately.

The primary analysis will be performed under the intention-to-treat framework on the full analysis set of patients (FAS) that includes all randomised patients (regardless of whether they have received treatment). Patients who discontinue study medication will be followed until the end of the trial. Patients who are lost to follow-up for vital status will be censored for the primary endpoint at the time of their last known vital status. All patients will be analysed according to the treatment arm to which they were randomised.

For the comparison of 110mg DE-DAT vs warfarin-TAT, patients of all ages and geographical regions will be included. For the comparison of 150mg DE-DAT vs warfarin-TAT, patients from the EU/ROW who are ≥80 years old will be excluded from the warfarin-TAT arm (as patients who are ≥80 years old from the EU/ROW are not randomised to 150mg DE-DAT).

The robustness of the primary analysis will be assessed by an on-treatment analysis. This on-treatment analysis will only count events that occur while a patient is taking study medication (including the REP of 6 days – see [Section 5.2.2.2](#)). It will also analyse patients by the actual treatment that was being taken while the event occurred.

Proprietary confidential information.

© 2016 Boehringer Ingelheim International GmbH or one or more of its affiliated companies. All rights reserved.

This document may not - in full or in part - be passed on, reproduced, published or otherwise used without prior written permission.

In addition, a sensitivity analysis will be performed that censors patients who switch from dabigatran to non-study warfarin or from study warfarin to non-study NOAC, at the time of the switch. The proportional hazards assumption will be investigated.

Kaplan-Meier curves will also be presented.

Subgroup analyses are planned and will be specified in the Trial Statistical Analysis Plan (TSAP).

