7.5 RANDOMISATION

Patients aged <80 years old will be randomly assigned to 110mg DE-DAT, 150mg DE-DAT or warfarin-TAT in a 1:1:1 ratio for the duration of the trial.

Proprietary confidential information.

© 2016 Boehringer Ingelheim International GmbH or one or more of its affiliated companies. All rights reserved.

This document may not - in full or in part - be passed on, reproduced, published or otherwise used without prior written permission.

Patients aged ≥ 80 years old will be randomly assigned depending on their geographical region:

- Patients aged ≥ 80 years old in the USA will be assigned to 110mg DE-DAT, 150mg DE-DAT or warfarin-TAT in a 1:1:1 ratio
- All other patients aged ≥ 80 years old (i.e. EU/ROW) will be assigned to 110mg DE-DAT or warfarin-TAT in a 1:1 ratio.

Patients will be randomised in permuted blocks, dynamically stratified by age (< 80 or ≥ 80 years old) and region (EU/ROW or USA) using an IRT. Dynamic stratification allocates blocks of randomisation numbers according to the strata of the first randomised patient within that block. For example, if the first patient randomised to the first block is < 80 years old and from the USA, other randomisation numbers within this block will only be allocated to patients < 80 years old from the USA (until there are no more randomisation numbers left to allocate within this block). BI will arrange for the packaging and labelling of study medication. The randomisation list will be generated using a validated system and a pseudo-random number generator so that the resulting treatment will be both reproducible and non-predictable. The block size will be documented in the CTR. Access to the codes will be controlled and documented.

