4. CHANGES IN THE PLANNED ANALYSIS OF THE STUDY

During the course of the study, the DMC may advise to stop enrolment into certain treatment arms or to stop the study completely. For further information, see CTP [5], Section 7.3.4. Changes to the planned analysis were introduced in protocol amendments 1 and 2. In addition, some further changes were implemented as follows.

Due to the Japanese local amendment (where the randomisation age group stratification factor was changed from <80 or ≥80 years old to <70 or ≥70 years old for Japanese patients), it will be necessary to change the way the age group stratification factor is defined in the analysis. Instead age group will be changed to be non-elderly vs. elderly and this will be used as the stratification factor in some analyses.

Due to the relatively few numbers of elderly patients finally recruited in the US region, it will not be possible to fit an age-group stratified Cox proportional hazards regression model for the 150mg DE-DAT versus warfarin-TAT comparison for any of the endpoints. Instead an unstratified model will be applied comparing 150mg DE-DAT versus warfarin-TAT. (excluding elderly EU/ROW patients in the warfarin-TAT group). In addition, unstratified sensitivity analyses of the non-elderly stratum only will be conducted.

GI bleeds, MBEs (ISTH), CRNMBEs, life-threatening bleeds and fatal bleeds were added as other safety endpoints.

The further endpoint of hospitalisation and the further composite endpoint of all-cause death or hospitalisation were added at the request of the Executive Steering Committee on 22nd November 2016.

The sensitivity analysis that censors patients who switch from study dabigatran to non-study NOAC/VKA or from study warfarin to non-study NOAC/VKA, at the time of the switch plus the Residual Effect Period (REP) of 6 days will not be performed because it will be virtually identical to the on-treatment sensitivity analysis already planned.

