7.4 PRIMARY ENDPOINT

This is a prospective, randomised, open label, blinded endpoint (PROBE), active comparator trial and the clinical endpoints are being adjudicated by an IAC in a blinded fashion. The IAC

Charter contains details of the outcome event adjudication criteria. The study will employ a time to first event analysis (using a stratified Cox proportional hazards regression model) and it is assumed that all patients will be observed until first primary endpoint event or until the last patient entered has completed at least six months of treatment (up to an anticipated maximum duration of approximately 30 months for the first patient entered). The trial will be monitored by an independent DMC.

This study is designed to test two safety hypotheses in NVAf patients that have undergone a successful PCI (elective or due to ACS) with stenting and were treatment naïve or were receiving oral anticoagulant treatment (either with warfarin, another VKA or other novel oral anticoagulant) before the procedure.

The primary endpoint, measured from date of randomisation to end of observation period, is:

- Time to first ISTH MBE or CRNMBE

as determined by the IAC. Only positively adjudicated events will be included in the analyses. They will be analysed using the stratified Cox proportional hazards regression model including age group (non-elderly or elderly [<70 or ≥ 70 years old in Japan and <80 or ≥ 80 years old everywhere else]) as a stratifying factor and treatment arm (110mg DE-DAT vs warfarin-TAT and 150mg DE-DAT and 110mg DE-DAT combined vs warfarin-TAT). For the 150mg DE-DAT versus warfarin-TAT comparison, an unstratified model will be applied comparing 150mg DE-DAT versus warfarin-TAT (excluding elderly EU/ROW patients in the warfarin-TAT group). In addition, an unstratified sensitivity analysis of the non-elderly patients only will be conducted.

Models will be fitted for each comparison separately (110mg DE-DAT vs warfarin-TAT and 150mg DE-DAT vs warfarin-TAT). The Breslow method [9] will be used to handle tied failure times.

The primary analysis will be performed under the intention-to-treat framework on the FAS. Patients who discontinue study medication will be followed until the end of the trial for vital status, ECGs, AEs, OEs (including completion of the bleeding questionnaire) and concomitant medications. All patients will be analysed according to the treatment arm to which they were randomised.

Survival time

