A summary of adjudication will be presented showing the number of investigator-reported OEs along with whether they were positively or negatively adjudicated or whether they were non-assessable. Further analyses will be performed on investigator reported events (i.e. those that are positively and negatively adjudicated). A sensitivity analysis will be performed that includes any non-assessable events into the positively adjudicated MBE/CRNMBE category.

Two safety hypotheses (110mg DE-DAT vs. warfarin-TAT and 150mg DE-DAT vs. warfarin-TAT) will be tested:

1. 110mg DE-DAT is non-inferior to warfarin-TAT with respect to MBE/CRNMBE over the duration of the trial

2. 150mg DE-DAT is non-inferior to warfarin-TAT with respect to MBE/CRNMBE over the duration of the trial.

To control the Type I error rate at a one-sided 0.025 level, a hierarchical procedure for multiple testing will be used to test the above hypotheses. Additional testing for safety and efficacy endpoints will also be included in this hierarchical procedure. The following hierarchical procedure will be applied:

Step 1 – Non-inferiority of 110mg DE-DAT to warfarin-TAT in MBE/CRNMBE is met at the one-sided 0.025 level of significance

Step 2 – Non-inferiority of 150mg DE-DAT to warfarin-TAT in MBE/CRNMBE is met at the one-sided 0.025 level of significance

Step 3 – Non inferiority of 150mg DE-DAT and 110mg DE-DAT combined to warfarin-TAT in DTE and unplanned revascularisation by PCI/CABG is met at the one-sided 0.025 level of significance

Step 4 – Superiority of 110mg DE-DAT to warfarin-TAT in MBE/CRNMBE is met at the one-sided 0.025 level of significance

Step 5 – Non inferiority of 150mg DE-DAT and 110mg DE-DAT combined to warfarin-TAT in DTE is met at the one-sided 0.025 level of significance

Step 6 – Superiority of 150mg DE-DAT to warfarin-TAT in MBE/CRNMBE is met at the one-sided 0.025 level of significance

If any of the steps above fail to meet statistical significance, the testing procedure will stop at that step and subsequent tests will not be performed.

The Non-Inferiority (NI) margin used will be 1.38 (on the relative hazard ratio (HR) scale). See Section 7.6 of the CTP for a clinical justification of this margin. The upper bound of the Wald confidence interval (CI) of the HR of DE-DAT vs. warfarin-TAT (one-sided 97.5%) will be compared to this NI margin for the NI testing.

Kaplan-Meier survival figures will be presented by treatment group/strata and by treatment group.

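### The SAP's AE/SAE tables and overall Kaplan-Meier figure state no matched warfarin group for 150mg, although the 150mg Cox comparison uses one

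*SAP*

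**What the plan says.** **Allocation.** Protocol 3.1 and 7.5 randomise patients under 80, and US patients of 80 or over, equally to three arms. Other patients of 80 or over "will be assigned to 110mg DE-DAT or warfarin-TAT in a 1:1 ratio". SAP 4 adds that for Japan "the randomisation age group stratification factor was changed from <80 or ≥80 years old to <70 or ≥70 years old for Japanese patients", and SAP 7.4 defines elderly as 70 or over in Japan and 80 or over elsewhere. SAP 4 also notes that few elderly US patients were recruited.

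**Model-based comparison.** Protocol 7.3.1 says that, for 150mg against warfarin, EU/ROW patients of 80 or over "will be excluded from the warfarin-TAT arm". SAP 7.4 repeats this with its own definition of elderly: "excluding elderly EU/ROW patients in the warfarin-TAT group". SAP 7.8.5 applies the primary endpoint's methods to the other bleeding endpoints.

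**Descriptive outputs.** SAP 7.8 states: "All safety analyses will be performed on the TS (including the REP, where applicable"). The Treated Set in SAP 6.3 has no age or region limit. SAP 7.8.1 states "Adverse events per patient year will be summarised by treatment, primary system organ class (SOC) and preferred term (PT"), and for the rate, "The number of events per patient year is calculated per treatment arm as follows". It also plans separate SAE summaries. For the primary endpoint, SAP 7.4 plans: "Kaplan-Meier survival figures will be presented by treatment group/strata and by treatment group". None of these sentences restricts warfarin for the 150mg comparison. SAP 7.8.1 leaves table templates to the technical TSAP, which is not among the documents.

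**The concern.** The exclusion in the Cox comparison exists because 150mg and the whole warfarin arm do not come from the same randomised population. Warfarin includes elderly non-US patients, and 150mg has none. That applies equally to a rate in an AE table or to an overall survival curve. AE analyses are descriptive, so no model puts it right afterwards.

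Protocol 7.3.3 gives comparison of AE incidence between arms as the purpose of these tables, so a reader will set the 150mg column against the warfarin column printed beside it. For an event that rises with age, this flatters the higher dose and can shrink or hide a real excess. In a trial whose primary question is safety, that is the unfavourable direction for an error.

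**Working it through.** **The plan's own figure.** The plan gives no figure for this quantity. Its design figure does reproduce: with 334 events and margin 1.38, √334/2 × ln 1.38 − 1.96 = 0.98, which is 83.7% power against the stated 83.6%. This point does not touch it.

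**Inputs from the documents.** 1:1 allocation (110mg or warfarin) for elderly non-US patients; 1:1:1 for everyone else; 14% pooled one-year risk of the primary endpoint (protocol 7.6).

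**Assumed inputs.** e, the share of all randomised patients who are elderly and non-US: 5-20%. k, the risk of an event in those patients relative to the others: 1.25-2.0. Mean exposure is taken as equal in the two groups, so that patient shares also serve as exposure shares in the per-patient-year table.

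**Step 1: elderly non-US share of warfarin.** s = (e/2) / (e/2 + (1−e)/3). At e = 10% this is 0.05/0.35 = 14.3%. In 150mg it is 0%.

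**Step 2: displayed ratio with no drug effect.** Ratio of 150mg to full warfarin = 1/(1 + s(k−1)).

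| e | s | k = 1.25 | k = 1.5 | k = 2.0 |
|---|---|---|---|---|
| 5% | 7.3% | 0.98 | 0.97 | 0.93 |
| 10% | 14.3% | 0.97 | 0.93 | 0.88 |
| 15% | 20.9% | 0.95 | 0.91 | 0.83 |
| 20% | 27.3% | 0.94 | 0.88 | 0.79 |

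At k = 1 the ratio is 1.00. Against warfarin without the elderly EU/ROW patients it is 1.00 for every e and k.

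**Step 3: effect on a real excess.** A true ratio of 1.10 is displayed as 1.10 times the table entry: 1.08 (e = 5%, k = 1.25), 1.03 (10%, 1.5) or 0.97 (20%, 1.5).

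**Step 4: ceiling for common events, n (%) tables only.** A proportion cannot exceed 1, so k ≤ 1/p, where p is the proportion affected among the other patients. At an assumed p = 0.70, k ≤ 1.43, and the null ratio cannot fall below 0.97 (e = 5%) or 0.90 (e = 20%). This limit does not apply to the per-patient-year table, whose denominator is exposure days.

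**Step 5: overall Kaplan-Meier figure.** Assume constant hazards, k now as a hazard ratio, and no drug effect. Choose the non-elderly hazard h so that (1−e)(1−exp(−h)) + e(1−exp(−hk)) = 0.14. The 150mg risk is 1−exp(−h). The full-warfarin risk is (1−s)(1−exp(−h)) + s(1−exp(−hk)).
- e = 10%, k = 1.5: 13.4% against 14.3% at one year, a gap of 0.9 points.
- e = 20%, k = 2: 11.9% against 14.8%, a gap of 2.9 points.

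**The case against.** The strongest reply is that column layout belongs in table templates. SAP 7.8.1 sends those to the technical TSAP, and SAP 6.4 and 7.6 are redacted, so a matched column may exist where it cannot be seen. That stands as a limit: the finding is that the SAP states no matched comparator, not that the tables will lack one. It does not remove the point. Which patients form the comparator decides what the table means, and the SAP fixes that for the Cox model.

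Second, the age effect is documented only for major bleeding: protocol 4.2.2.1 describes higher risk from age 75 with antiplatelets or strong P-gp inhibitors. After randomisation, bleeds, deaths, MIs and strokes are recorded as outcome events and not as SAEs (protocol 5.2.2.2), and the bleeding endpoints have matched hazard ratios. This stands, so age dependence of the remaining AEs is an assumption.

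Third, SAP 7.4 also plans curves by stratum and a non-elderly sensitivity analysis, and SAP 7.1 tabulates demographics by arm. An attentive reader can therefore see the imbalance. This lowers the priority but does not make the unmatched overall curve a randomised comparison.

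Some stronger inferences are not supported:
- A reader might infer that the 150mg non-inferiority or superiority tests are biased. They are not, because they use the matched group.
- A reader might infer that the event counts and percentages in SAP 7.5.2 share the fault. That section adopts the primary endpoint's methods, which carry the exclusion, so no change is needed there.
- A reader might take it as stated that Japanese patients aged 70-79 cannot receive 150mg. The local amendment is not shown. This is an inference from the changed stratification factor and the elderly definition in SAP 4 and 7.4.

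**Conclusion.** The point holds for descriptive outputs only: the AE and SAE tables of SAP 7.8.1 and the overall Kaplan-Meier figure of SAP 7.4. Followed as written, they set 150mg against a warfarin arm that includes a group of patients who could not have been randomised to 150mg. The direction is in favour of 150mg for events that rise with age; where there is no age effect there is no bias.

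The size cannot be derived from the documents. The range of 0.98 to 0.79 rests wholly on the assumed elderly share, the assumed risk ratio and equal exposure, and nothing in the documents favours one part of it. For common events in n (%) tables the lower values cannot occur. Confirmatory tests, hazard ratios and stratified curves are unaffected. Priority: minor.

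**What to change.** - In the AE and SAE tables of SAP 7.8.1, add a column for warfarin-TAT excluding elderly EU/ROW patients, with elderly as defined in SAP 7.4. Name it as the comparator for 150mg, and keep the full warfarin arm as the comparator for 110mg.
- In SAP 7.4, draw the overall 150mg Kaplan-Meier curve against the same matched group.
- If the technical TSAP already has this column, one sentence in SAP 7.8.1 citing it is enough for the tables.

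The cost is one extra column or curve per affected output. No new data are needed and no test changes.

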7.3.3 Safety analyses

Safety endpoints are defined in [Section 5.2.1](#).

These endpoints will be analysed using the same methods as the primary endpoints. No multiplicity adjustments are planned for safety endpoints (apart from those mentioned in the hierarchy, see [Section 7.2](#)).

Proprietary confidential information.

© 2016 Boehringer Ingelheim International GmbH or one or more of its affiliated companies. All rights reserved.

This document may not - in full or in part - be passed on, reproduced, published or otherwise used without prior written permission.

Adverse events will be coded using the Medical Dictionary for Regulatory Activities (MedDRA) coding dictionary. Standard BI summary tables and listings will be produced to compare the incidence of AEs. All AEs with an onset after the first dose of study medication up to the end of the REP of 6 days (see [Section 5.2.2.2](#)) after the last dose of study medication will be assigned to the treatment period for evaluation. Other adverse events will be assigned either to the screening or post study period as appropriate.

On-treatment analyses will be performed for AEs.

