7.6 DETERMINATION OF SAMPLE SIZE

This is an event-driven trial where it is assumed that the first patient recruited into the study will be followed up for a maximum of approximately 30 months and the last patient recruited into the trial will be followed up for a minimum of 6 months. It is assumed that patient accrual will be approximately uniform over the 24 month recruiting period.

The proportion of patients with at least one MBE/CRNMBE at one year is estimated to be 14% based on current blinded trial data.

A relative NI margin for the original co-primary endpoint (DTE) was chosen in analogy to recent SPAF trials with primary endpoints of stroke/SE, where 1.38 was used by the FDA for ximelagatran, apixaban, rivaroxaban and dabigatran to preserve at least 50% of the relative reduction (on the log scale) in the risk associated with warfarin in six previous (historical), randomised, controlled trials. See publication by Jackson K, Gersh BJ, Stockbridge N, et al. [[R08-2662](#)]. The same NI margin has been applied to MBE/CRNMBE as it was considered the most clinically relevant available reference in the absence of any other type of data.

The overall sample size is driven by the non-inferiority comparison of MBE/CRNMBE between 110mg DE-DAT or 150mg DE-DAT and warfarin-TAT. With $\alpha=0.025$ (one-sided) and 14% of patients with at least one event at one year, 334 patients with at least one MBE/CRNMBE in each pair of treatment groups (i.e. 167 patients with MBE/CRNMBE per treatment group) are required to achieve 83.6% power for this endpoint, yielding a final sample size estimated at 834 patients in each treatment group (i.e. 2502 randomised patients in total). Therefore approximately 500 patients with at least one MBE/CRNMBE are required in total across the three treatment groups.

Proprietary confidential information.

© 2016 Boehringer Ingelheim International GmbH or one or more of its affiliated companies. All rights reserved.

This document may not - in full or in part - be passed on, reproduced, published or otherwise used without prior written permission.

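### SAP 7.8.1 calls its adverse event measure events per patient-year, but the formula counts patients with an AE over total exposure, so label and formula disagree

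*SAP*

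**What the plan says.** SAP 7.8.1 makes the "number (and %) of patients with AEs and not on the number of AEs" the basis of all AE analyses. It then adds that, beyond the usual summaries, "some analyses will be based on the number of AEs per patient year". The tabulation by treatment, system organ class (SOC) and preferred term is described as adverse events per patient-year, and the formula is introduced with "The number of events per patient year is calculated per treatment arm as follows". The section thus names the measure as a count of events three times.

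The formula itself is "total number of patients with AE" × 365.25 / number of days exposure. Section 7.8.1 neither defines days of exposure nor refers to another section for it. It closes with "Further details will be provided in the technical TSAP", meaning table lists, templates and dataset specifications.

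SAP 7.7 defines duration of exposure as last dose date minus first dose date plus 1. "Total treatment time therefore includes time when treatment was temporarily discontinued and subsequently reintroduced"; a second version that takes interruptions into account is also computed, without the REP. Neither version stops at the first AE. SAP 6.1 and Protocol 7.3.3 assign AEs in the 6 days after the last dose to the treatment period. Protocol 7.3.3 states the purpose: "Standard BI summary tables and listings will be produced to compare the incidence of AEs".

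**The concern.** Two rates are in common use for AEs. An event rate is the number of AEs divided by total exposure. A first-event incidence rate is the number of patients with the AE divided by time at risk up to first onset. The formula takes its numerator from the second and, on the natural reading, its denominator from the first. A patient with five episodes adds 1 to the numerator, and the time after the first episode stays in the denominator.

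If the tables carry the SAP's wording, a reader would take a common row as an event rate and understate how often the AE occurs. Contrasts between arms in those rows would also look smaller than they are. What is at stake is the reading of descriptive safety tables for common AEs and SOC totals, not any confirmatory result.

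**Working it through.** **Plan's own figure.** The documents give no AE rate, so there is no figure to reproduce. The label/formula mismatch follows from the text alone; only its size needs assumptions.

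**Ordering.** For one table row, let P = patients with the AE, E = AEs, T = total exposure and T1 = exposure up to first AE. The SAP figure is P/T, the event rate E/T and the first-AE rate P/T1. Over one and the same window P ≤ E and T1 ≤ T, so P/T cannot exceed either rate. Because P cannot exceed the number of patients, P/T also cannot exceed 1 / mean exposure, which is 1/1.5 = 0.67 per patient-year at 18 months.

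**Inputs.**
- Exposure: uniform over 0.5 to 2.5 years, mean 1.5. Protocol 7.6 has follow-up from 6 to about 30 months and assumes "patient accrual will be approximately uniform over the 24 month recruiting period"; Protocol 3.2 gives an estimated average of 18 months. This is participation, used as a stand-in for drug exposure.
- Patients per arm: 834 (Protocol 7.6), for illustration.
- AE rate λ: assumed constant, 0.02 to 1.0 per patient-year.

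**Formula.** Proportion of patients with the AE: p(λ) = 1 − (e^(−0.5λ) − e^(−2.5λ)) / (2λ). SAP figure: p(λ)/1.5. Under a constant rate both proper rates equal λ.

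**Worked case, λ = 0.5.** p = 1 − (0.7788 − 0.2865)/1 = 0.5077. In 834 patients that is 423 patients with the AE, 0.5 × 1251 = 626 AEs, 1251 patient-years of exposure and 423.4/0.5 = 847 patient-years at risk. SAP figure 423/1251 = 0.338; event rate 626/1251 = 0.500; first-AE rate 423/847 = 0.500.

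| True rate per year | Patients with AE | SAP figure | Shortfall |
|---|---|---|---|
| 0.02 | 2.9% | 0.0197 | 2% |
| 0.05 | 7.2% | 0.048 | 4% |
| 0.2 | 25.4% | 0.169 | 15% |
| 0.5 | 50.8% | 0.338 | 32% |
| 1.0 | 73.8% | 0.492 | 51% |

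**Repeat AEs clustered in some patients** (gamma frailty, variance 1, assumed), mean rate 0.2: the SAP figure is 0.150, which is 25% below the event rate of 0.2 and 14% below the first-AE rate of 0.174.

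**Between arms.** The displayed ratio is p(1.5λ)/p(λ) when the true ratio is 1.5 and exposure is equal. At λ = 0.5: p(0.75) = 1 − (0.6873 − 0.1534)/1.5 = 0.644, and 0.644/0.5077 = 1.27. At control rates 0.05, 0.2, 0.5 and 1.0 the displayed ratio is 1.47, 1.39, 1.27 and 1.15.

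**REP mismatch.** If AEs in the 6-day REP are counted but REP days are left out of the denominator, the figure rises by about 1% or less. It then slightly exceeds the first-AE rate in very rare rows: by 0.7% when 0.75% of patients have the AE and by 0.2% at 1.5%, with the crossover near 2%.

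**The case against.** The strongest reply is that this is terminology. The formula states its numerator openly and follows the section's own rule of counting patients, and patients per total exposure is a well-defined quantity. That is fair as far as it goes: nothing is miscalculated, and relabelling alone would settle the mismatch.

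A reader might infer from the patient-counting rule that the label must be the error. The documents do not settle this. The section names an event measure three times and introduces it as an addition to the usual patient-based summaries, so the numerator could equally be the slip.

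The first-AE half of the point is an inference. Section 7.8.1 does not refer to 7.7, and the technical TSAP is not available. Total exposure is the likeliest reading, since no definition in the SAP stops at the first AE. Which of the two 7.7 versions applies may be settled in the technical TSAP, so silence on that is not counted as a defect. Table headings and footnotes may also differ from the SAP text, but the SAP states label and formula itself, and these would still conflict.

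A reader might also infer that the figure is always below the first-AE rate. It need not be in very rare rows, because of the REP mismatch shown above.

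Finally, the sizes rest on assumed rates, and participation overstates drug exposure. If half the patients stopped early, the shortfall at 0.5 per year would be 29% instead of 32%. That trims the effect without removing it.

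**Conclusion.** The point holds. As written, SAP 7.8.1 produces a number that is not what its label says. It is not an event rate and, if exposure is as in SAP 7.7, not a first-AE incidence rate. For common AEs and SOC totals it lies below both; for rare preferred terms the gap is negligible. The percentages depend on the assumed constant rates and on uniform 6-to-30-month exposure, while the mismatch itself depends on no assumption.

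A reader might infer that comparisons between arms are safe because both use the same formula. That is close to true when the true rates are equal: with 30% of one arm stopping early, the displayed ratio stays within 0.96 to 1.00. It is not true when the rates differ, because the formula then attenuates the ratio. A reader might equally infer that the trial's conclusions are affected. The documents do not support that. AE tables are descriptive, no hypothesis test uses the formula, and bleeds, deaths, MI, stroke, SE, TIA and stent thrombosis are collected as outcome events (Protocol 5.2.2.2) with their own analyses. This is a correction worth making, of low severity.

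**What to change.** The sponsor should state which measure is meant and make label and formula agree, in one of three ways:

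- **(a) Event rate.** Replace the numerator with the number of AEs and keep total exposure as the denominator.
- **(b) Incidence rate.** Keep patients with the AE and divide by summed time at risk for each SOC and preferred-term row, from first dose to first onset or, if there is none, to the end of the on-treatment period including the REP. Label it as patients with AE per patient-year at risk. This removes dependence on exposure length fully only under a constant hazard, so it should be read beside the exposure table.
- **(c) Minimum.** Keep the calculation and label it as patients with AE per patient-year of total exposure.

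In each case, use the same window, with or without the 6-day REP, for numerator and denominator, and name the SAP 7.7 exposure version unless the technical TSAP already does.

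Cost: (c) changes text and, where needed, table headings, plus the denominator if REP days must be added. (a) needs modest reprogramming. (b) needs an at-risk time for every row, with more programming and checking. None needs new data.
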